An AE will be considered treatment emergent (TEAE) if it begins or worsens in severity after the first dose of the double-blind Study Treatment through 28 days after the last dose of Study Treatment, or the date of initiation of another investigational agent or surgical intervention. Each AE is to be evaluated for date/time of onset, duration, ocular versus non-ocular, severity, outcome and causal relationship with the study drug or other factors.

	
Sponsor: Aldeyra Therapeutics, Inc. Sponsor Protocol No. ALDNS2-203-D1

--	---

Derived and Imputed Data

TEAEs will be assigned to a treatment based on the time of occurrence in relation to the last treatment administered prior to the onset of the TEAE. Time since last dose at time of onset will be calculated as the difference between the onset date and time and the date and time of the last dose of the treatment at onset. Time since last dose will be expressed in days, hours and minutes. Duration will be calculated for AEs that resolve as the difference between the resolution date and time and onset date and time. Duration will be expressed in days, hours and minutes.

Based on the MedDRA preferred term, subjects who experience the same AE on multiple occasions will be summarized at the maximum severity and most conservative relationship to the study medication. If 2 or more AEs are reported as a single event, the individual terms will be reported as separate AEs.

Serious Adverse Events

Serious adverse events (SAEs) are those events recorded as a “serious Adverse Event (Y)” on the adverse events page of the CRF. A summary of serious TEAEs and Serious treatment related TEAEs by SOC and PT will be prepared.

Adverse Events Leading To Death

Adverse events leading to death are those events with ‘Death’ recorded under Outcome in the adverse events page of the CRF. A summary of TEAEs and SAEs leading to death by SOC and PT will be prepared. A listing of AEs leading to death will be included with the TEAEs flagged.

Data Summarization

TEAEs will be classified and summarized according to the treatment at onset of the AE. The summary of TEAEs after the study drug administration on Visit 3 of Treatment Period 1 will be presented grouped by three treatments.

The AEs will be summarized by MedDRA system organ class and preferred term for each treatment group.

Treatment-emergent AEs (TEAEs) will be tabulated separately for safety population overall, and for ocular/non-ocular, by treatment group:

	
Sponsor: Aldeyra Therapeutics, Inc. Sponsor Protocol No. ALDNS2-203-D1

--	---

- Summary of TEAEs categorized by death, serious AEs, leading to withdrawal and related to study drug (safety/ocular/non-ocular)
- Summary of TEAEs by system organ class and MedDRA preferred term (safety/ocular/non-ocular)
- Summary of TEAEs by severity (safety)
- Summary of TEAEs by relation to study drug (safety)

Adverse events will be listed as:

- Adverse events by subject and AE number
- Adverse events that caused the subject to discontinue
- Serious AEs

Severity.

Severity is classified as mild, moderate or severe. Missing severity for TEAEs will be counted as severe.

Adverse events with a missing relationship to study medication will be noted as “related” to study medication. If a patient reports the same AE more than once within the same SOC/PT, the AE with the strongest relationship to study medication will be used in the relationship summaries.

Pregnancies

Urine pregnancy tests will be performed from Screening Visit 1 through final treatment Visit 5. Pregnancy test results will be listed by subject and visit.

Vital signs

Blood pressure (systolic and diastolic, mm Hg), pulse rate (beats/min), respiratory rate (breaths/min) and body temperature (degree Celsius) will be assessed from Screening Visit 1 to final treatment Visit 5. The vital signs at EEC Visit 5 will be assessed at pre and post EEC time points, whereas the vital signs at EEC Visit 3 and Visit 4 will only be made at pre EEC time point. All vital signs data will be listed by subject, visit and time point as applicable.

Fundus Assessment

Fundus assessment will be performed at Screening Visit 1 to final treatment Visit 5, and will be listed by subject, visit and eye.

	Sponsor: Aldeyra Therapeutics, Inc. Sponsor Protocol No. ALDNS2-203-D1
---	---

Intraocular Pressure Readings (IOP)

Non-contact tonometry (NCT) assessment will be performed at Screening Visit 1 and at Visit 3 to Visit 5 to measure the Intraocular Pressure (IOP). The collected data (average of 3 readings for each eye) will be listed by subject, treatment, visit and time point as applicable. Summary statistics of the average of 3 IOP readings for treatment Visit 3 to Visit 5 for each eye will be tabulated by treatments and time points and presented for both Right and Left eyes.

Visual Acuity (VA)

VA assessment will be performed at each visit. Data will be listed by subject, visit, treatment, time point and eye as applicable. Summary statistics of Visual Acuity for treatment Visit 3 to Visit 5 will be tabulated by treatment and eye.

Slit lamp Assessment

[figure not shown]
Slit lamp assessment will be performed at each visit. Data will be listed by subject, visit, treatment, time point and eye as applicable. Abnormalities and clinically significant findings will also be listed.

CHANGE TO THE PLANNED ANALYSES

The final version of the protocol specified additional efficacy assessments for Post-EEC exit time points. However, the list of efficacy endpoints in the protocol do not cover the data related to these Post-EEC exit time points. Therefore, the following additional efficacy endpoints were added in the SAP.

- AUC 0-274 mins for Itching on VAS scale
- AUC 0-274 mins for Itching on 9 points scale
- AUC 0-270 mins for Conjunctival Redness on 9 points scale
- AUC 0-274 mins for TOSS

	
Sponsor: Aldeyra Therapeutics, Inc. Sponsor Protocol No. ALDNS2-203-D1

--	---

TABLES, LISTINGS AND FIGURES (TLFs)

The TLFs shells for this study is provided in a separate document SAP Mock TLFs. The shells may change due to unforeseen circumstances such as data formatting. These shells may not be reflective of every aspect of this study but are intended to show the general layout of the Tables, Listings and Figures that will be included in the final report. TLFs are numbered following the E3 "Structure and Content of Clinical Study Report".

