1.5 Minimization of Risk

In clinical trials with Reproxalap Ophthalmic Solution in various strengths in different ocular indications, no safety signal or treatment related SAEs have been observed (Section 1.3.1).

While subjects are in the EEC, they will be exposed to ragweed pollen for approximately 3.5 hours and are expected to experience allergy symptoms (itchy eyes, watery eyes and eye redness and/or itchy nose, nasal congestion, runny nose, sneezing) typically experienced during the ragweed pollen season. They will be receiving either active or vehicle treatment that may or may not relieve their allergy symptoms to a certain degree. Subjects will be monitored with regular medical health checks during the EEC Sessions in this study and will be treated according to the investigator's evaluation. Subjects with known anaphylactic reactions and moderate to severe asthma are excluded from this trial, please defer to detailed inclusion and exclusion criteria. The revised crietria allowing screened failed subjects to be reconsidered for the trial, is not anticipated to introduce any additional known risks, Subjects will have washed out from prior ragweed exposure

Some known risks are also associated with skin prick testing like soreness, minor bruising, redness and/or irritation (itching, burning and/or stinging) at the site where the skin test is done. A very rare severe allergic reaction, anaphylaxis can occur. It may be life threatening with clinical signs and symptoms such as breathing difficulties, hives, swelling of the skin or tongue, itchy skin, or a decrease in blood pressure. The clinical staff on site is trained per site medical SOPs. Emergency care is available on-site to treat, if an allergic reaction or anaphylaxis develop.

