7.6 Adverse Events

AEs will be collected from the time the subject signs the informed consent form through 30 days after the last dose of IP. AEs must be recorded in the CRF. The Sponsor and investigator or qualified site staff will review and evaluate AEs on an ongoing basis. See [Section 9](#) for further detail on AE reporting.

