8.1 Medical Screening Visit (Visit 1)

- Obtain written informed consent ([Section 7.1](#))
- Review eligibility criteria ([Section 7.2](#))
- Collect demographic information and document medical and social history ([Section 7.3](#))
- Perform physical examination ([Section 7.4](#))
- Collect concomitant medications ([Section 7.5](#))
- Perform VA, SLE, NCT, and dilated fundoscopy ([Section 7.10](#))
- Collect vital signs and samples for laboratory testing ([Sections 7.7 and 7.8](#))
- Collect urine sample for pregnancy test, if applicable ([Section 7.8.3](#))
- Perform skin prick test ([Section 7.9](#))

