8.2 Screening EEC Visit (Visit 2)

- Review eligibility criteria ([Section 7.2](#))
- Collect concomitant medications and adverse events ([Sections 7.5 and 9](#))
- Collect vital signs and perform urine pregnancy test ([Sections 7.7 and 7.8.3](#))
- Perform VA and SLE and fundus examination ([Section 7.10](#))
- Obtain symptom collection (staff-assess and subject-reported) pre- and post-EEC entry ([Section 7.11](#))
- 
- EEC session ([Section 7.12](#))

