9 ADVERSE EVENT REPORTING

AEs will be collected from the time the subject signs the informed consent form through 30 days after the last IP administration.

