9.1.1.1 Events Not to Be Considered as Adverse Events

Pre-existing medical conditions/signs/symptoms present before the EEC Screening Visit (Visit 2) that do not worsen in severity or frequency during the clinical trial are defined as baseline medical conditions, and are not to be considered AEs.

Pregnancies are not considered AEs but must be reported, see [Section 9.1.8](#).

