9.1.5 Reporting Serious Adverse Events

The investigator is responsible for reporting all SAEs, regardless of causality, to the Sponsor designee within 24 hours of learning of the occurrence. SAEs should be sent to: Inflamax Research Limited.

(Local toll-free numbers will be provided on the SAE report form cover sheet.)

The reporting timeframe starts when the subject signs the informed consent or assent form through 30 days after the last IP administration. At a minimum, a description of the event and the Investigator's judgment of causality must be provided at the time of the initial report. These preliminary reports will be followed by detailed descriptions that will include copies of hospital case reports, autopsy reports, and other documents when requested and applicable.

A follow-up SAE Report must be submitted within 24 hours of the investigator receiving the follow-up information (such as information regarding complications, progression or resolution).

An SAE that is considered completely unrelated to a previously reported event should be reported separately as a new SAE.

The procedures for reporting SAEs are as follows:

- Complete the “Serious Adverse Event Report Form.” The investigator may contact Pharmacovigilance via the telephone hotline for assistance with SAE reporting.
- Fax or email the SAE Form to the attention of Pharmacovigilance within 24 hours of the investigator's knowledge of the event.

The original copy of the SAE Report Form and the fax confirmation sheet (or email) must be kept with the source documentation at the clinical trial site.

Follow-up information should be communicated the same way, using a new SAE Report Form stating that it is a follow-up to the previously reported SAE and giving the date of the original report. The follow-up information should describe whether the event has resolved or continues, if and how it was treated, and whether the subject continued or withdrew from clinical trial participation.

The investigator and qualified site staff should institute any supplemental investigations of SAEs based on their clinical judgment of likely causative factors. This may include clinical laboratory tests not specified in the protocol, histopathologic examinations, or consultations with specialists. The Sponsor or their designee may also request the investigator to conduct supplemental assessments.

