1. A Visual Analog Scale (VAS) measured on a 0- 100 mm continuous scale where 0 is considered no itching and 100 is considered maximum itch.

[REDACTED]

Sponsor: Aldeyra Therapeutics, Inc.
Sponsor Protocol No. ALDNS2-203-D1

Ocular Tearing

[REDACTED]

[REDACTED]

[REDACTED]

[REDACTED]

[REDACTED]

[REDACTED]

VIII. SAFETY ASSESSMENTS

Safety assessments will include the following:

- Visual Acuity (VA) for Visit 1 through Visit 5.
- Slit Lamp Examination (SLE) for Visit 1 through Visit 5.
- Non-Contact intraocular pressure Tonometry (NCT) during Visit 1 and Visit 3 to Visit 5.
- Dilated Fundus Examination as Screening Visit 1 and Visit 5 and undilated Fundus examination at Visit 2, 3 and 4.
- Vital Signs (VS) for Visit 1 to Visit 5.
- Safety Clinical Laboratory parameters at Screening Visit 1 and at Visit 5.

	
Sponsor: Aldeyra Therapeutics, Inc. Sponsor Protocol No. ALDNS2-203-D1

--	---

- Adverse Events (AEs: reported, elicited and observed) from Visit 2 through Visit 5.

IX. ANALYSIS POPULATIONS

SAFETY POPULATION

All randomized subjects who received at least one dose of IP, regardless of whether clinical trial assessments were performed.

INTENT-TO-TREAT (ITT) POPULATION

All randomized subjects who received at least one dose of IP and have any post-dose assessments. Subjects are evaluated according to the IP treatment of the visit as per the randomized treatment sequence.

COMPLETER POPULATION

COMPLETER population will include all randomized subjects who received IP dosing at all three EEC treatment visit.

PER-PROTOCOL (PP) POPULATION

All ITT subjects will be considered PP if IP dosing occurs and do not have a major deviation from the protocol. The following is a list of protocol violations which would exclude subjects from the PP population:

- Subject did not receive IP as assigned.
- Subject did not meet all inclusion/exclusion criteria.

X. ENDPOINTS

EFFICACY ENDPOINTS

The following efficacy endpoints will be derived for each pharmacodynamic measures in each treatment visit and will be used to assess the activity of Reproxalap Ophthalmic Solutions.

- AUC 0-212 mins for Itching on VAS scale
- AUC 0-212 mins for Itching on 9 points scale
- AUC 0-210 mins for Conjunctival Redness on 9 points scale
- AUC 0-212 mins for Tearing on 4 points scale
- AUC 0-212 mins for TOSS
- AUC 0-92 mins for Itching on VAS scale

	Sponsor: Aldeyra Therapeutics, Inc. Sponsor Protocol No. ALDNS2-203-D1
--	---

- AUC 92-212 mins for Itching on VAS scale

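### Do the differing adverse-event windows in the protocol and SAP leave the safety analysis undefined?

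*SAP*

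**What the plan says.** **Collection period.** Protocol 7.6: "AEs will be collected from the time the subject signs the informed consent form through 30 days after the last dose of IP". Protocol 9 says the same. For serious events, 9.1.5 has: "The reporting timeframe starts when the subject signs the informed consent or assent form through 30 days after the last IP administration".

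**Visits.** SAP VIII, in its list of safety assessments, has "Adverse Events (AEs: reported, elicited and observed) from Visit 2 through Visit 5". The synopsis and Protocol 2.3 also place AE assessments at Visits 2 to 5. The Visit 1 list (8.1) has no AE item; the Visit 2 list (8.2) has "Collect concomitant medications and adverse events".

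**Baseline conditions.** Protocol 9.1.1.1 removes from the AE definition: "Pre-existing medical conditions/signs/symptoms present before the EEC Screening Visit (Visit 2) that do not worsen in severity or frequency during the clinical trial".

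**Treatment-emergent window.** SAP XII runs from the first dose to 28 days after the last dose, or to the start of another investigational agent or a surgical intervention. Protocol 9.1.2 bounds it only by the duration of the trial. Protocol 10.5 gives no end, but leaves the description of all safety evaluations to the SAP.

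**Headline safety variable.** Protocol 10.5 names the incidence of subjects with any AE over the whole trial.

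**The concern.** Read side by side, the documents seem to offer two starts (consent, Visit 2) and three ends (Visit 5, 28 days, 30 days). Safety and tolerability are stated objectives, and the headline variable in Protocol 10.5 covers the whole trial, so its value could depend on the window an analyst picks.

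Two consequences would matter. If Visit 5 were a data cut-off, delayed events after the last session would be lost, because Visit 5 is both the last dosing visit and the exit visit. If the Visit 2 baseline rule were applied strictly, events caused by screening procedures would disappear. The protocol itself foresees such events in 1.5: "Some known risks are also associated with skin prick testing like soreness, minor bruising, redness and/or irritation".

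**Working it through.** **1. Sort the statements by what they define.**

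| Question | Where | Answer |
|---|---|---|
| Over what period are AEs collected? | Protocol 7.6, 9, 9.1.5 | Consent to last dose + 30 days |
| At which visits are they assessed? | Synopsis, Protocol 2.3, SAP VIII | Visits 2 to 5 |
| Which count as treatment-emergent? | SAP XII | First dose to last dose + 28 days |
| What is baseline rather than an AE? | Protocol 9.1.1.1 | Present before Visit 2 and not worsening |

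The first three rows are compatible. SAP VIII is a visit-by-visit list (visual acuity, tonometry, fundus and so on), and its AE line is one more entry. Events since consent can be picked up at Visit 2. SAP XII confirms that SAP VIII is not a cut-off: for a subject last dosed at Visit 5, a 28-day window presupposes data after Visit 5.

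**2. End of the window.** 30 − 28 = 2 days. An event on day 29 or 30 is collected but falls outside the TEAE tables. An analysis window inside a collection window is not a contradiction, and SAP I gives the SAP precedence on statistical methods.

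**3. Start of the window.** The fourth row does conflict with the first.
- Visit 1 to Visit 2: 2 days to 8 weeks (synopsis) = 2 to 56 days.
- Consent to first dose, adding about 14 days to Visit 3: 2 + 14 = 16 to 56 + 14 = 70 days.

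A new event in the 2 to 56 days that does not worsen is collected under 7.6 and is not an AE under 9.1.1.1. Its effect on planned output:
- It precedes dosing, so it is not a TEAE under Protocol 9.1.2 or SAP XII.
- SAP XII assigns each TEAE to the last treatment given before onset; here there is none.
- If it worsens after dosing, the 9.1.1.1 exemption no longer applies and it becomes a TEAE under either reading.
- In a screen failure it enters no safety table, because the Safety Population is randomised and dosed.

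**4. Stated duration.** Protocol 3.5 gives about 14 weeks. The longest screening interval plus three two-week intervals is 56 + 42 = 98 days = 14.0 weeks, ending at Visit 5. Adding 30 days gives 128 days = 18.3 weeks; with 2-day screening it is 2 + 42 + 30 = 74 days = 10.6 weeks. Section 3.5 describes the five clinic visits, so it does not contradict later AE collection.

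**5. Worst case, if Visit 5 were a cut-off.** The last named assessment is at 274 minutes after chamber entry (SAP X); doses are at about −5 and 95 minutes. Follow-up of the last session would be 274 − 95 = 179 minutes (3.0 h) from the second dose and 274 + 5 = 279 minutes (about 4.7 h) from the first. With 75 subjects and no dropout this affects 25/75 = 33% of each treatment's exposures. The sequences ABC, BCA and CAB put each treatment last once, so the loss would be roughly balanced. Step 1 shows that this reading does not fit the SAP.

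**The case for a change.** The best argument for acting is that 9.1.1.1 is a definition, not a visit schedule, so reading Visits 2 to 5 as elicitation visits does not remove the conflict. Protocol 9.1.1 adds to it by defining an AE in a patient given investigational product, which read literally excludes everything before Visit 3. The whole-trial count in 10.5 then has no single start, and two programmers could follow the documents and differ. The visible text also does not say how new AEs in the 30 days after Visit 5 are found, and SAP XII gives alternative TEAE end points without saying that the earliest applies.

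The textual conflict stands, but its reach is short. No visible SAP table computes the whole-trial count; the planned tables are of TEAEs, and 10.5 leaves safety evaluation to the SAP. At most, a pre-treatment event would appear or not appear in a listing. The missing Visit 1 item and the missing later contact cannot be established, because Protocol 7 makes Table 1 the governing schedule and Table 1 is not shown. Taking the earliest of the alternative TEAE end points is the natural reading. Nothing in the documents makes 30 days better than 28 for the analysis; after single-day dosing sessions that choice is a preference.

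**Conclusion.** No change to the plan is needed. The real inconsistency is confined to new, non-worsening events in the 2 to 56 days between Visits 1 and 2, and it leaves the TEAE tables and every treatment comparison of AEs as they are. An analyst can resolve it by listing events between consent and first dose apart from the TEAEs. The 2-day difference between collection and TEAE windows is harmless. The remaining differences come from stating visits in one place and periods in another.

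This rests on three assumptions: SAP VIII is read as a list of visits, as its layout and the SAP's own 28-day rule indicate; the redacted parts of the SAP add no analysis of pre-dose AEs; and the 30-day collection required by Protocol 7.6 and 9 is carried out, by whatever contact Table 1 provides.

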2.4 Exploratory Efficacy Endpoints

The following endpoints will be derived for each treatment visit and will be used to assess the activity of Reproxalap Ophthalmic Solutions.

- AUC 0-212 mins for Itching on VAS scale
- AUC 0-212 mins for Itching on 9 points scale
- AUC 0-210 mins for Conjunctival Redness on 9 points scale
- AUC 0-212 mins for Tearing on 4 points scale
- AUC 0-212 mins for TOSS
- AUC 0-92 mins for Itching on VAS scale
- AUC 92-212 mins for Itching on VAS scale
- AUC 0-32 mins for Itching assessed by VAS Scale
- AUC 32-72 mins for Itching assessed by VAS Scale

All 0 time-point measurements will be pre-EEC entry/ baseline values. All the time-points are approximate values.

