Adjustments for Multiplicity	24
Interim Analysis	25
General Considerations	25
Subject Populations and Disposition.....	25
Discontinuations	26
Protocol Deviations/Violations.....	26
Data Sets Analyzed	26
Demographic and Other Baseline Characteristics	26
Pre-ecr MEASUREMENT for Visit 3, 4 and 5	27
Medical History And Concomitant Diseases.....	27
Concomitant Medication	27
Study Drug Administration	28
Efficacy Analyses.....	28
Safety Analyses	30
Change to the Planned Analyses.....	33
Appendix 1: Calculations.....	34
Tables, Listings and Figures (TLFs)	34

	Sponsor: Aldeyra Therapeutics, Inc. Sponsor Protocol No. ALDNS2-203-D1
---	---

I. INTRODUCTION

The purpose of the statistical analysis plan (SAP) is to describe the planned analyses and reporting for protocol 18-MO-001:

“An Exploratory Clinical Trial Evaluating Reproxalap Ophthalmic Solutions (0.25% And 0.5%) In Subjects With Seasonal Allergic Conjunctivitis Using The Environmental Exposure Chamber (EEC)”

This SAP is being written with due consideration of the recommendations outlined in the most recent International Council on Harmonization (ICH) E9 Guideline entitled Guidance for Industry: Statistical Principles for Clinical Trials and the most recent ICH E3 Guideline, entitled Guidance for Industry: Structure and Content of Clinical Study Reports (CSR).

This SAP is a summative and definitive plan, based on the final protocol dated November 22, 2018 (Version FINAL 4.0).

The SAP includes details of data handling procedures and statistical methodology. The SAP also outlines the statistical programming specifications for the Tables, Listings and Graphs (TLGs). No interim analysis is planned for this study.

The final statistical analysis will proceed exactly according to the SAP approved by the sponsor as well as by Inflamax Research.

The statistical analysis methods presented in this document will supersede the statistical analysis methods in the clinical protocol. If additional analyses are required to supplement the planned analyses described in the SAP, they will be labeled as post-hoc and will be identified in the CSR.

Responsibilities

Inflamax Research will perform the statistical analyses described herein and is responsible for the production and quality control (QC) of tables, figures, and listings associated with the analyses other than the post hoc analyses.

II. STUDY DESIGN

OVERVIEW OF STUDY DESIGN AND DOSING REGIMEN

ADX-102-AC-011/18-MO0001 is a single center study.

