- AUC 0-32 mins for Itching assessed by VAS Scale
- AUC 32-92 mins for Itching assessed by VAS Scale
- AUC 0-274 mins for Itching on VAS scale
- AUC 0-274 mins for Itching on 9 points scale
- AUC 0-270 mins for Conjunctival Redness on 9 points scale
- AUC 0-274 mins for TOSS

Since there are time windows available for symptom assessments, all time points above refers to the planned nominal time points and the actual elapsed time points may differ from the nominal time points. For detailed derivations of these parameters, please see SAP Appendix 1, Calculations.

SAFETY ENDPOINTS

- Adverse Events/Adverse Drug Reactions
- Intraocular Pressure Readings (IOP)
- Visual Acuity (VA)

XI. STATISTICAL METHODOLOGY

Summary Statistics

Unless the list of summary statistics is specified for any summary table, the standard summary statistics that will be calculated for quantitative and qualitative variables are:

Quantitative: sample size (number of subjects), mean, median, standard deviation, minimum and maximum of the raw data

Qualitative: sample size (number of subjects), absolute and relative frequencies per class

The summarization will be done by three treatment groups and at every scheduled time point (if applicable) for every endpoint.

Reporting Precision

Summary statistics will be presented to the following degree of precision:

	Sponsor: Aldeyra Therapeutics, Inc. Sponsor Protocol No. ALDNS2-203-D1
--	---

Statistics	Degree of precision
Mean (of all kinds), Median, Quartiles, Confidence Intervals	one more than the raw data
Standard deviation, Standard error	two more than the raw data
Minimum, Maximum	the same as the raw data
P-value	rounded to 3 decimal places and therefore presented as 0.xxx; P-values smaller than 0.001 as '<.001'
Percentage, Coefficient of variation	one decimal place

Fractional numeric values will be presented with a zero to the left of the decimal point (for example, 0.12 - 0.30, not .12 - .30).

Common Definitions and Labels

Study Day is the number of days since administration of study drug during a Treatment Period, which is counted as Study Day 1. Study Day is derived separately for each of the 3 treatments.

Nominal Time is the scheduled measurement time relative to the dose time.

Study Time or Actual Elapsed Time is the time from the last administration of study drug. So, for example, if study drug is administered at 08:00 on Day 1, 10:00 on Day 1 represents a study time (or actual elapsed time) of 2:00 hours.

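### The SAP lists VAS itching AUC 32-92 where the protocol lists AUC 32-72, and does not declare the difference

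*SAP*

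**What the plan says.** **Protocol.** The endpoint lists in the synopsis (Statistical Analysis) and in section 2.4 both contain nine AUC endpoints and both end with "AUC 32-72 mins for Itching assessed by VAS Scale".

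**SAP section X (Efficacy Endpoints).** The first eight entries match the protocol, including "AUC 0-92 mins for Itching on VAS scale" and "AUC 0-32 mins for Itching assessed by VAS Scale". The ninth is "AUC 32-92 mins for Itching assessed by VAS Scale". Four AUCs running to 270 or 274 minutes follow.

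**SAP, *Change to the Planned Analyses*.** The only reason given for departing from the protocol is that "the list of efficacy endpoints in the protocol do not cover the data related to these Post-EEC exit time points". It continues "Therefore, the following additional efficacy endpoints were added in the SAP" and names the four long AUCs. Neither 32-72 nor 32-92 appears.

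**SAP section I.** The plan is "based on the final protocol dated November 22, 2018 (Version FINAL 4.0"), and its methods "will supersede the statistical analysis methods in the clinical protocol". It also commits the final analysis to follow the SAP exactly, with anything further labelled post hoc.

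**The concern.** The SAP has a section for declaring changes to the endpoints and uses it for four of them. A reader will take that list as complete and conclude that the other nine endpoints are the protocol's own. One is not.

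Two things follow. AUC 32-72 drops out of the planned output. The record of pre-specification is also turned round: the protocol-listed window could be reported only as post hoc, while the window absent from the protocol would appear as planned. The trial names no primary endpoint and makes no multiplicity adjustment, so the credibility of any single window rests largely on a traceable endpoint list.

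**Working it through.** The plan gives no power or error-rate figure that bears on this point, so there is none to reproduce. The check compares the lists and then asks how far apart the two windows are.

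**1. Compare the lists** (Protocol synopsis and section 2.4; SAP section X; SAP *Change to the Planned Analyses*).

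| Endpoint | Protocol | SAP | Declared as a change |
|---|---|---|---|
| VAS itching 0-212, 0-92, 92-212, 0-32 | yes | yes | not needed |
| 9-point itching 0-212; redness 0-210; tearing 0-212; TOSS 0-212 | yes | yes | not needed |
| VAS itching 32-72 | yes | no | no |
| VAS itching 32-92 | no | yes | no |
| VAS itching, 9-point itching and TOSS 0-274; redness 0-270 | no | yes | yes |

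Protocol: 8 + 1 = 9. SAP: 8 + 1 + 4 = 13. Dropped: 9 - 8 = 1. New: 13 - 8 = 5, of which 4 are declared and 1 is not.

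**2. Can AUC 32-72 be recovered from the other SAP endpoints?** The SAP's VAS windows are 0-212, 0-92, 92-212, 0-32, 32-92 and 0-274. Their edges are 0, 32, 92, 212 and 274. None is at 72, so no sum or difference of these AUCs gives 32-72.

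**3. What do the plan's own rules then require?** SAP section I fixes the analysis to the SAP. Protocol sections 10.1 and 10.4 and SAP section I label anything beyond it post hoc. AUC 32-72 is therefore not produced as planned, and if produced it is post hoc.

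**4. How different are the two windows?** 72 - 32 = 40 minutes; 92 - 32 = 60 minutes; 92 - 72 = 20 minutes are not shared. The itching schedule (Table 3) and Appendix 1 are not visible, so the next step is an assumption: readings every 10 minutes from 32 to 92, equal variance at each, trapezoidal AUC.

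- Weights for 32-92: 5, 10, 10, 10, 10, 10, 5 (sum 60).
- Weights for 32-72: 5, 10, 10, 10, 5 (sum 40).

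With a common correlation r between readings, and unit variance:

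- covariance = r × 60 × 40 + (1 - r) × 375
- variance of 32-92 = r × 60² + (1 - r) × 550
- variance of 32-72 = r × 40² + (1 - r) × 350

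At r = 0.3: 982.5 / √(1465 × 725) = 0.953. The other cases were computed in the same way:

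| Assumed structure | Correlation of AUC 32-92 with AUC 32-72 |
|---|---|
| common r = 0.3 / 0.5 / 0.8 | 0.953 / 0.975 / 0.993 |
| autoregressive, 0.7 / 0.9 / 0.97 per 10 minutes | 0.942 / 0.979 / 0.994 |

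Over these assumptions the range is 0.94 to 0.99.

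**The case against.** **The SAP may hold the intended window.** With 32-92, the windows 0-32, 32-92 and 92-212 divide the session without a gap and break shortly before the second dose at about 95 minutes. With 32-72, minutes 72 to 92 fall in no sub-window except 0-92. A typing error in the protocol is therefore as plausible as one in the SAP. This stands, and for that reason the protocol cannot simply be declared right. It might explain the difference but does not declare it.

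**The SAP has precedence and is itself pre-specified.** The protocol delegates detail to a SAP finalised before database lock and unmasking, and the SAP says its methods override the protocol's. A window fixed in such a SAP is still pre-specified, so the gap is one of traceability. But the override clause speaks of analysis methods, and the SAP recorded its other endpoint changes separately.

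**Nothing is irretrievable.** The SAP plans summaries by scheduled time point and listings of all scores, so AUC 32-72 stays computable. That is true, but under the plan's rules it would be a post hoc result.

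**Stronger readings that the documents do not support.**
- A reader might infer that 32-92 merely duplicates other endpoints. It equals neither AUC 0-92 nor AUC 0-32. It is their difference if the AUC is linear with a reading at 32 minutes, and its standard error and p-value do not follow from theirs without the covariance. The protocol already has a similar dependency, since 0-212 is the sum of 0-92 and 92-212.
- A reader might treat the longer window as the size of the harm. A larger AUC from more minutes reflects only the length, and nothing in the plan compares the two windows.
- A reader might suspect a data-driven choice, because SAP section VI refers to an observed discontinuation rate and so was worded during the trial. Both documents keep the sponsor masked until database lock, and nothing shows that the window was chosen on results.

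**Conclusion.** The plan is wrong as written, at low severity. One of nine protocol endpoints is replaced in the SAP, and the replacement is the only one of five new SAP endpoints that is not declared. Which window was intended cannot be settled from the documents.

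The effect on conclusions is probably small. The trial is exploratory, with no formal hypothesis, and no sample size or error rate depends on this endpoint. The correlation of 0.94 to 0.99 rests on an assumed reading grid and assumed correlation structures, and it does not exclude a treatment effect that differs in minutes 72 to 92.

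One reservation remains. The version number of the protocol text is not visible, so a difference from the version that the SAP cites cannot be fully excluded. It is unlikely: this protocol fits the SAP's description of the final version, with post-exit assessments but no endpoint beyond 212 minutes.

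**What to change.** Before unmasking, reconcile the two documents:

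1. State which window was intended.
2. Keep VAS itching AUC 32-72 in SAP section X as the protocol-listed endpoint.
3. If 32-92 is wanted, report it as well and list it, with its reason, under *Change to the Planned Analyses*.
4. If 32-72 was a typing error in the protocol, say so in that section.

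This takes a line in the endpoint list and a line or two in the change section. Both AUCs come from the same itching assessments, so no new data are needed. The downside is one more exploratory AUC in the tables.
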